6.3 Withdrawal criteria

Subjects are free to withdraw from the study at any time, without prejudice to their continued care.

Subjects should be withdrawn from the study if any of the following events occur:

1. Subject withdraws his/her consent.
2. The Sponsor or a regulatory agency requests withdrawal of the subject.
3. Subject is noncompliant with the study procedures or medications in the opinion of the Investigator.
4. Subject and/or Investigator do(es) not think that PSL is effective (ie, lack or loss of efficacy).
5. Subject cannot tolerate the minimum PSL dose of 50mg bid (100mg/day).
6. Subject takes prohibited concomitant medications, prescribed or over-the-counter as defined in this protocol.
7. A prolongation or worsening of overall seizure duration, frequency, type, or pattern considered by the Investigator as serious enough to warrant discontinuation from the study.
8. Subjects with an echocardiogram showing a Grade 2 finding (moderate regurgitation/stenosis) if accompanied with moderate to severe signs/symptoms or a Grade 3 finding (severe regurgitation/stenosis) will be discontinued from the study regardless of accompanying clinical symptoms, and should begin discontinuation of PSL. Additionally, a jump of 2 grades from Grade 0 to Grade 2 (moderate regurgitation/stenosis) accompanied with moderate to severe symptoms or from Grade 1 to Grade 3 (severe regurgitation/stenosis) will result in subject discontinuation (see [Section 6.3.2](#)).
9. Changes in the ECG that are regarded as clinically significant and/or that worsens over time.
 - An ECG shows an absolute value for QTcB or QTcF ≥ 500 ms or ≥ 60 ms above Baseline.
 - Subject develops second- or third-degree atrioventricular block or another clinically-relevant change in ECG as determined by the Investigator.
10. [REDACTED] as indicated by a positive response (“Yes”) to Question 4 of the “Since Last Visit” version of the C-SSRS. The subject should be referred immediately to a mental healthcare professional and may be withdrawn from the study based upon the Investigator’s judgment of the benefit/risk ratio of continuing the subject in the study on PSL.

- [REDACTED] as indicated by a positive response (“Yes”) to Question 5 of the “Since Last Visit” version of the C-SSRS. The subject should be referred immediately to a mental healthcare professional and must be withdrawn from the study.
11. Subject develops an illness that would interfere with his/her continued participation.

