 12. For subject developing psychiatric/mood/behavioral signs or disturbances (see examples in list below) that are clinically concerning or that worsen over time, the PSL dose should be gradually reduced and, if symptoms persist, withdrawal from the study should be considered. The subject should be referred to a mental health professional, and continuation of PSL should only be allowed with the approval and under close oversight of the mental health specialist, and upon confirmation of the positive benefit/risk by the Investigator.
 - Auditory or visual hallucinations
 - Delusions/paranoia/grandeur
 - Disorganized thought process
 - Agitation/aggression/apathy
 - Dysphoria/depression/mood lability/euphoria
 - Disinhibition
 - Cognitive changes/memory impairment/delirium
 - Aberrant motor behavior
 13. Subject is suspected of having a serious multiorgan hypersensitivity reaction. Serious suspected multiorgan hypersensitivity cases may be identified and reported to the Sponsor by the Investigator using the following algorithm:
 - An AE or laboratory value (as defined below) suggestive of internal organ involvement including but not limited to hepatitis, nephritis, pneumonitis, carditis, colitis, encephalitis, pancreatitis, myositis, arthritis, or hematologic system involvement combined with at least one of the following: fever, rash, lymphadenopathy, or eosinophilia.
 - Treatment-emergent abnormal laboratory value criteria suggestive of internal organ involvement or eosinophilia:
 - Eosinophils percentage $\geq 10\%$
 - Eosinophils absolute $\geq 0.5\text{G/L}$
 - Neutrophils absolute $< 1.5\text{G/L}$
 - Platelets absolute $\leq 100\text{G/L}$
 14. There is confirmation of a pregnancy during the study, as evidenced by a positive pregnancy test.

Investigators should attempt to obtain information on subjects in the case of withdrawal or discontinuation. For subjects considered as lost to follow up, the Investigator should make an effort (at least 1 phone call and 1 written message to the subject), and document his/her effort

(date and summary of the phone call and copy of the written message in the source documents), to complete the final evaluation. All results of these evaluations and observations, together with a narrative description of the reason(s) for removing the subject, must be recorded in the source documents. The eCRF must document the primary reason for withdrawal or discontinuation.

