#### 3.2.3.1 Mapping of assessments performed at early discontinuation

Unlike other scheduled visits, an early discontinuation visit (EDV) doesn't have a predetermined visit window and can occur at any days during the study. If an EDV occurs at the day of a scheduled visit, in-clinic safety assessments such as vital signs, ECGs, and blood collection for clinical laboratory assessments, should correspond to that scheduled visit. In-clinic safety assessments at an EDV that occurs on a day between two scheduled visits will be assigned to the next scheduled clinic visit. All other efficacy assessments and questionnaire collected on an EDV will not be mapped.

In the by-visit summary tables, only nominal (scheduled) visits where the assessment is scheduled will be included. Unscheduled visits will not be mapped to scheduled visits. In the subject listing, data will be presented under the actual visits, including EDV and unscheduled visits.

Seizure data collected by diary are associated with periods defined within the study and as such there is no need to map them to visits. If a subject withdraws between visits an effort is made to recover all diary records for use in calculation of seizure frequencies.

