## 3.3 Definition of Baseline values

Baseline refers to the baseline of the parent study unless noted otherwise.

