### 9.5.2 Electrocardiograms

The following ECG parameters will be recorded: heart rate, PR-interval, QRS-duration, QT-interval, QTcB [QT corrected for heart rate using Bazett's formula] or QTcF [QT corrected for heart rate using Fridericia's formula], and Investigator's conclusion on ECG profile.

The 12-Lead ECG results are collected at Entry Visit, Visit 3, Visit 5 and at visits every 6 months thereafter. An ECG at the SFU will be performed only if abnormal at EOS or EDV Visit.

For each ECG, the overall ECG result, is also collected, categorized by the investigator as one of: no abnormality, an abnormal but not clinically significant finding, or a clinically significant finding.

QTcB and QTcF will also be presented by following classification per visit:

- Observed results:  $<450\text{ms}$ ,  $450-<480\text{ms}$ ,  $480-<500\text{ms}$  and  $\geq 500\text{ms}$
- Change from Baseline:  $<30\text{ms}$ ,  $30-<60\text{ms}$ ,  $\geq 60\text{ms}$

The observed ECG parameter values and their absolute change from Baseline will be summarized (SS) descriptively for each scheduled assessment visit, as well as Last Visit, maximum value, and minimal value.

The number and percentage of subjects with no abnormality, an abnormal but not clinically significant finding, and a clinically significant finding will be summarized for each of the scheduled assessment visits. Percentages for the visit will be relative to the number of subjects with an ECG result for the visit.

The number and percentage of subjects with an abnormal ECG value described in Appendix 13.3 will be summarized for the overall and by 3-month interval during the Exposure Period. Subject numbers for those meeting the abnormal criteria will also be presented.

All 12-Lead ECG parameters will be listed per visit, including the change from baseline and a abnormality criteria flag. In addition, the data from patients with at least one finding will be listed with the finding.

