### 13 APPENDICES

#### 13.1 LABORATORY ASSESSMENTS – PCST

The following criteria will be applied in the determination of possibly clinically significant treatment emergent laboratory assessment values.

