### 13.3 ELECTROCARDIOGRAM (ECG) – ABNORMAL

Abnormality criteria to be applied in the assessment of ECG parameter values are given below:

Parameter	Age	Abnormality Criteria
QT interval (ms)	1m-<12y	>500
	>12y	>500 or ≥60ms increase from Baseline
QTc(F) (ms)	<6m	>490, or >15% increase from Baseline
	6m-<3y	>440, or >15% increase from Baseline
	3y-<12y	>440, or >15% increase from Baseline
	>12y- <17y	>440, or >15% increase from Baseline
	≥17y	>500 or ≥60ms increase from Baseline
QTc(B) (ms)	<6m	>490, or >15% increase from Baseline
	6m-<3y	>450, or >15% increase from Baseline
	3m-<12y	>450, or >15% increase from Baseline
	>12y- <17y	>450, or >15% increase from Baseline
	≥17y	>500 or ≥60ms increase from Baseline
PR interval (ms)	<6m	>150, or >25% increase from Baseline
	6m-<3y	>170, or >25% increase from Baseline
	3y-<12y	>180, or >25% increase from Baseline
	>12y - <17y	>200, or >25% increase from Baseline
	≥17y	Treatment-emergent value >200, >220, >250
QRS interval (ms)	<6m	>90, or >25% increase from Baseline
	6m-<3y	>90, or >25% increase from Baseline
	3y-<12y	>100, or >25% increase from Baseline
	>12y - <17y	>110, or >25% increase from Baseline
	≥17y	Treatment-emergent value >100, >120, >140
Heart rate (bpm)	<6m	<100, >180
	6m-<3y	<90, >150
	3y-<12y	<60, >130
	>12y	<50, >120

Abbreviations: bpm = beats per minute; m = months; ms = milliseconds; QTc = corrected QT interval; y = years. A month is defined as 30 days; a year is defined as 365.25 days.

Note: Treatment-emergent is defined as meeting the criteria at any post-Baseline visit during EP0093 (including unscheduled visits) and not meeting the same criteria during Baseline in the parent study.

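### SAP Appendix 13.3 flags adult QTc only above 500 ms where protocol criterion 9 and SAP 9.5.2 start at 500 ms, and the SAP laboratory list omits the absolute eosinophil value in protocol criterion 13

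*SAP*

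**What the plan says.** **QTc.** Protocol section 6.3, criterion 9, covers the case where "An ECG shows an absolute value for QTcB or QTcF" of 500 ms or more, or at least 60 ms above Baseline. For age 17 and over, SAP Appendix 13.3 sets the abnormality criterion for QTcF and for QTcB at ">500 or ≥60ms increase from Baseline". SAP 9.5.2 uses that appendix for one table, overall and by 3-month interval: "The number and percentage of subjects with an abnormal ECG value described in Appendix 13.3". It also specifies a second display: "QTcB and QTcF will also be presented by following classification per visit". The top level category there is 500 ms or more, and the top change category is 60 ms or more.

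**Laboratory.** Protocol section 6.3, criterion 13, concerns a suspected serious multiorgan hypersensitivity reaction. Under the label "Treatment-emergent abnormal laboratory value criteria suggestive of internal organ involvement or eosinophilia" it lists four values: eosinophils at least 10%, absolute eosinophils at least 0.5 G/L, neutrophils below 1.5 G/L, and platelets at or below 100 G/L. SAP Appendix 13.1 opens with "The following criteria will be applied in the determination of possibly clinically significant treatment emergent laboratory assessment values". Its hematology table (13.1.1) has the eosinophil percentage, the neutrophil cut-off and the low platelet cut-off at the same values. It has no row for the absolute eosinophil count. SAP 9.3 summarizes subjects who meet these criteria (PCST) overall and by 3-month interval.

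**The concern.** Long-term safety is the primary objective, and protocol 12.3 plans only descriptive methods for it. The cut-offs therefore decide what is reported. Protocol 12.3 also plans a listing and a summary of possible clinically significant treatment-emergent laboratory abnormalities. The SAP list that delivers this leaves out a value that the protocol itself groups under that kind of heading.

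For QTc, the SAP uses two boundaries within one section, and the appendix boundary differs from the protocol's. Section 3.9 of the SAP, on changes to protocol-defined analyses, mentions neither difference. At stake are a small undercount in one ECG table and a larger set of eosinophil counts that no laboratory flag picks up.

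**Working it through.** There is no power, alpha or sample-size figure to reproduce. The check compares the rules directly.

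**QTc**

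Inputs:
- Protocol rule (criterion 9): QTc ≥ 500 ms, or QTc − Baseline ≥ 60 ms.
- SAP flag (Appendix 13.3): QTc > 500 ms, or QTc − Baseline ≥ 60 ms.
- Baseline: SAP 3.3 states "Baseline refers to the baseline of the parent study unless noted otherwise". Criterion 9 does not say which Baseline it means, so the same value is assumed for both rules.

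Both rules were applied to every whole-millisecond pair with Baseline 350–499 ms and QTc 350–599 ms.

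1. The only QTc value that meets the protocol rule and misses the SAP flag is 500 ms.
2. It is missed only when 500 − Baseline < 60, that is, Baseline > 440 ms, or 441 ms and above in whole milliseconds. At Baseline 440 ms the rise is 60 ms and the reading is flagged.
3. Protocol 6.2 excludes QTc above 450 ms at entry to this study. The parent-study limit is not in the documents. If parent Baseline is assumed to be at most 450 ms, the missed Baselines are 441–450 ms. Without that assumption they are 441–499 ms over the range checked.
4. Every missed pair falls in the ≥ 500 ms category of SAP 9.5.2.
5. No pair is flagged by the SAP and missed by the protocol rule.

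The category display is per visit, and SAP 3.2.3.1 says that in by-visit tables "only nominal (scheduled) visits where the assessment is scheduled will be included". An unscheduled reading of exactly 500 ms with Baseline ≥ 441 ms is therefore outside the category display and unflagged by Appendix 13.3. It can still enter the maximum-value summary (SAP 3.2.4 and 9.5.2), and it appears in the ECG listing.

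**Eosinophils**

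The percentage equivalent to 0.5 G/L is 100 × 0.5 / WBC = 50 / WBC, with WBC in G/L. A count is unflagged when it is at least 0.5 G/L and the percentage is below 10. This requires 50 / WBC < 10, that is, WBC > 5.0 G/L.

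| WBC (G/L, illustrative) | 50 / WBC | Unflagged range |
|---|---|---|
| 4 | 12.50% | none |
| 5 | 10.00% | none |
| 6 | 8.33% | 8.33% to <10% |
| 8 | 6.25% | 6.25% to <10% |
| 10 | 5.00% | 5.00% to <10% |
| 12 | 4.17% | 4.17% to <10% |

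Appendix 13.1.1 leaves adult WBC itself unflagged from 3.0 to 12.0 G/L. Of that 9.0 G/L span, 12.0 − 5.0 = 7.0 G/L lies where the gap exists. This describes the span of values and not the share of subjects, because the documents give no WBC distribution.

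**The case against.** The strongest reply has four parts.

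- **Criterion 13.** A reader might infer that subjects with absolute eosinophils of 0.5 G/L or more have met a stopping criterion and vanish from the tables. The protocol does not support this. The withdrawal event is a suspected serious multiorgan hypersensitivity reaction. The algorithm requires evidence of organ involvement combined with fever, rash, lymphadenopathy or eosinophilia, so an isolated count is one component. This part of the reply stands in full.
- **QTc is covered elsewhere.** A reader might also infer that a subject withdrawn at 500 ms goes uncounted. At a scheduled visit the reading is in the ≥ 500 ms category. A withdrawn subject also appears in disposition by reason and, if an adverse event was the cause, among the TEAEs leading to discontinuation. This stands, except for the unscheduled reading described above.
- **The two QTc displays differ by design.** One is per visit, with level and change separate. The other combines level or change, overall and by interval. They would not match line for line even with identical cut-offs. This is correct, but it gives no reason for the level boundary itself to differ.
- **The lists are generic.** SAP 9.3 says the laboratory criteria come from FDA division guidelines with sponsor additions, and the age bands run from infancy. Nothing obliges them to mirror a withdrawal algorithm. This is fair as to origin. However, the list already matches the other three values of criterion 13, and no reason is given for leaving out the fourth. The laboratory shift table is not a secure substitute, because SAP 9.3 limits it to parameters in a Table 10-1 that the SAP does not contain.

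**Conclusion.** The concern holds as two limited inconsistencies.

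- **QTc:** Appendix 13.3 disagrees at one value with criterion 9 and with SAP 9.5.2. The effect is close to nil: a reading of exactly 500 ms, a rise under 60 ms, and a Baseline of at least 441 ms. This assumes whole-millisecond values and a common Baseline for both rules.
- **Eosinophils:** the omission is the larger part. It leaves counts of 0.5 G/L or more unflagged whenever WBC is above 5.0 G/L and the percentage is below 10. How many subjects that affects cannot be derived from the documents.

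Neither part shows that subjects who met a stopping rule go unreported. A reader might also see an error in the adult calcium row of Appendix 13.1.2, where the upper limit appears only in conventional units. That cell may have been lost in text conversion, and calcium is not a withdrawal criterion, so nothing is concluded from it.

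The documents show that the passages need reconciling. They do not settle which QTc threshold is clinically right, and this point takes no position on that.

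**What to change.** 1. In SAP Appendix 13.3, reconcile the adult QTcF and QTcB analysis flag with the ≥ 500 ms boundary used in SAP 9.5.2 and protocol criterion 9. With a ≥ 500 ms flag, the set of readings that meet the protocol rule and are not flagged becomes empty.
2. In SAP Appendix 13.1.1, add an analysis flag for absolute eosinophils at the value already stated in protocol criterion 13 (≥ 0.5 G/L). Footnote that it is one component of the hypersensitivity algorithm and that meeting it does not mean the subject met a withdrawal criterion.

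**Cost.** Two edits to the appendices and the matching flag programming. The QTc count will hardly change. The number of subjects flagged for eosinophils will rise, possibly more than slightly, and will include isolated values that do not lead to withdrawal. Both changes concern analysis flags only and leave the protocol's withdrawal rules as they are.

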### 13.4 Echocardiogram Valvular Abnormality Grading Criteria

Note: Based on the New York Heart Association Classification of symptoms. Other echocardiogram measurements are described in the study Echocardiogram Manual.

Echocardiogram Valvular Abnormality	Severity / Description	Potential Cardiovascular Signs/Symptoms	Action
Grade 0	Absent: no regurgitation, no stenosis	None reported	None
Grade 1	Mild: trace or barely detected regurgitation/stenosis	Minimal to none	None; continued observation
Grade 2	Moderate: regurgitation/stenosis with intermediate values	Symptoms: Shortness of breath on exertion or at rest; palpitation; syncope; anginal or pericarditic chest pain; fatigue or weakness	For a Grade 2/moderate severity, a decision to discontinue is based on severity of clinical signs/symptoms; if accompanied with moderate to severe signs/symptoms this results in subject discontinuation.
Grade 3	Severe: regurgitation/stenosis in the extreme range, often accompanied by other symptoms (eg, pulmonary congestion)	Signs: Pulmonary arterial pressure >40mm Hg and rise of >10mmHg; pulmonary edema; peripheral edema or ascites; atrial fibrillation or malignant arrhythmia; hypotension	Discontinuation of subject. For a Grade 3 of severe, subject should be discontinued regardless of accompanying clinical symptoms.
Grade increase by 2 levels	Increasing from: Grade 0 to 2 or Grade 1 to 3	Rapid onset of above signs/symptoms	A jump of 2 grades to Grade 2/moderate accompanied with moderate to severe

Echocardiogram Valvular Abnormality	Severity / Description	Potential Cardiovascular Signs/Symptoms	Action
			signs/symptoms results in subject discontinuation.  A jump of 2 grades to Grade 3/severe (with/without symptoms) will result in subject discontinuation.

This document cannot be used to support any marketing authorization application and any extensions or variations thereof.

REDACTED COPY

## **14 AMENDMENT(S) TO THE SAP**

### **14.1 Amendment 1**

#### **Rationale for the amendment**

The primary purpose of this amendment is to clarify details in the planned analyses and the early termination of the study.

#### **Modifications and changes**

##### **Major specific changes**

##### **Change #1**

**The following has been added:**

**Table 2-1: Schedule of assessments**

##### **Change #2**

**The following has been deleted:**

##### **2.2.2.1 Other efficacy variables**

Changes in drug load (ie, number of products, daily dose per given product, ratio of dose and Defined Daily Dose [WHO Collaborating Centre for Drug Statistics Methodology], frequency, drug class) of AEDs from Baseline to Visit 8, and to Visit 12 or EOS

##### **Change #3**

**The following has been deleted:**

##### **2.4 Determination of sample size**

The individual starting dose of each subject is 400 mg/day. This entry dose level was selected considering benefit-risk and is based on clinical pharmacology and positron emission tomography data in healthy human subjects. Once subjects enter EP0093, further individual dose adjustments are allowed between 100mg/day up to a maximum of 800mg/day to the extent possible with combination of tablet strengths available (ie, 25mg, 100mg, and 200mg). Integrity of the tablets should not be tampered with (eg, cut) to obtain lower dosages. More details on dosing can be found in the protocol in section 7.2

##### **Change #4**

**The following has changed:**

##### **3.2.2.2 Relative day**

Study day for each subject is calculated relative to the date of the first study visit (Entry Visit). The date format in the study is dd-MMM-yyyy. Relative day is calculated as the current date in

the study minus the date of the first study visit plus 1. For days after the last dose of study drug (during safety follow-up), relative day will be calculated as the current date minus the date of last dose of study drug and including a “+” to denote posttreatment days (e.g., the day after the last dose will be Day +1).

Generally, relative days for an event or measurement occurring during the study will be calculated as follows:

- $\text{Relative Day} = (\text{Event Date} - \text{Date of first visit}) + 1$

For events or measurements occurring after the date of last dose of study drug (as defined above), the relative day will be calculated with the date of last dose administration as Reference Date. Relative day in this case will be prefixed with ‘+’ in the data listings and will be calculated as follows:

- $\text{Relative Day} = + (\text{Event Date} - \text{Reference Date})$

All study level variables should be defined in subsections below. This includes analysis time points and definitions of study periods to be analyzed.

#### **Has been changed to:**

Relative days for an event or measurement occurring before the date of first dose of PSL in EP0093 will have a ‘-’ prefix and will be calculated as follows:

$\text{Relative Day} = -[(\text{Event date} - \text{Date of first dose})]$

Relative days for an event or measurement occurring on or after the date of first dose of PSL but not after the date of last dose of PSL in EP0093 will be calculated as follows:

$\text{Relative Day} = (\text{Event date} - \text{Date of first dose}) + 1$

For events or measurements occurring after the date of last dose of PSL in EP0093, relative day in this case will be prefixed with ‘+’ in the data listings and will be calculated as follows:

$\text{Relative Day} = + (\text{Event date} - \text{Date of last dose})$

All study level variables should be defined in subsections below. This includes analysis time points and definitions of study periods to be analyzed

